19.2. NIAID/FAAN Clinical Criteria for Anaphylaxis

From the Second Symposium on the Definition and Management of Anaphylaxis (Sampson, 2006).

*Anaphylaxis is highly likely when any **one** of the following 3 criteria are present*

1. Acute onset of an illness (minutes to several hours) with involvement of the skin, mucosal tissue, or both (e.g., generalized hives, pruritus or flushing, swollen lips-tongue-uvula)
AND AT LEAST ONE OF THE FOLLOWING
 - a. Respiratory compromise (e.g., dyspnea, wheeze-bronchospasm, stridor, reduced peak expiratory flow, hypoxemia)
 - b. Reduced blood pressure or associated symptoms of end-organ dysfunction (e.g., hypotonia [collapse], syncope, incontinence)

2. Two or more of the following that occur rapidly after exposure to a *likely allergen for that patient* (minutes to several hours):
 - a. Involvement of the skin-mucosal tissue (e.g., generalized hives, itch-flush, swollen lips-tongue-uvula)
 - b. Respiratory compromise (e.g., dyspnea, wheeze-bronchospasm, stridor, reduced peak expiratory flow, hypoxemia)
 - c. Reduced blood pressure or associated symptoms (e.g., hypotonia [collapse], syncope, incontinence)
 - d. Persistent gastrointestinal symptoms (e.g., crampy abdominal pain, vomiting)

3. Reduced blood pressure after exposure to *known allergen for that patient* (minutes to several hours):
 - a. Infants and children: low systolic blood pressure (age specific) or greater than 30% decrease in systolic blood pressure
 - b. Adults: systolic blood pressure of less than 90 mm Hg or greater than 30% decrease from that person's baseline

***Note:** Item 1 will generally apply to subjects in this study since SEL-037 will not be a known or a likely antigen for these subjects.

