For Cohorts 13, 15, and 17, SEL-110 will be administered prior to SEL-037. The rate of SEL-110 infusion will be 5.5 mL/hour for the first 30 minutes and, then, will be changed to a steady rate sufficient to deliver the remainder of the dose volume for the additional 25 minutes, concurrently with a 60 minute infusion of 125 mL of normal saline. The infusion of 0.2 mg/kg SEL-037 will delivered by infusion pump delivered over 60 minutes (+/- 2 minutes). If necessary, the infusion time may be extended in order to ensure the infusion of the study medication in entirety.

Distribution of Subjects

All enrolled subjects will be randomized initially to Cohorts 1, 2, 3 and 4 such that upon reaching 12 subjects total for all 4 cohorts, each cohort will contain 3 subjects. The experience of these 12 subjects will guide the further conduct of the study. Adverse events, safety labs and the rate of infusion reactions in individual cohorts will dictate the continuance of a specific cohort. After the completion of at least one treatment cycle the subject experience will be evaluated before enrollment is opened to all cohorts. The future enrollment will be randomized between all open cohorts.

At this time Cohorts 1-10 have been closed to enrollment. Randomization into the remaining open cohorts will continue until the cohorts are closed due to enrollment reaching 6-20 subjects per cohort or due to the stopping rules for individual cohorts. Cohorts that have closed due to enrollment levels may be re-opened to increase the enrollment to the maximum total number of subjects permitted.

Premedication for Study Drug Treatments

All subjects will receive 180 mg fexofenadine orally the night before receiving study drug (12 h \pm 2h) and again 2 \pm 1 hours before receiving study drug (ie. prior to SEL-037 for Cohorts 1 and 2 or SEL-110 for Cohorts 3-8, 10, 11, and 12). In addition, they will also receive methylprednisolone 40 mg (or equivalent drug, for example prednisone 50 mg IV or dexamethasone 8 mg IV) intravenously 1 \pm 0.5 hour before receiving study drug (ie. prior SEL-037 for Cohorts 1 and 2 or SEL-110 for Cohorts 3-8, 10, 11, 12, 13, 15, and 17). This will occur for every dose of study drug in Treatment Periods 1-5. These medications will be supplied by the clinic.

Premedication for Gout Flare

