 - Vitals at (Treatment Period 5, Day 0) predose (T-0), intradose after the start of study drug IV infusion (SEL-037) at 15, 30, 45, 60, 90, 120, and 180 minutes, then at 6 hours; and then at Treatment Period 5, Day 1, 7, 14, 21 and 30 or early termination
 - ECG exam at (Treatment Period 5, Day 0) predose and End of Study Treatment Period 5, Day 30 or early termination.
- Part B - Treatment period 5 - Cohort 3 (0.05 mg/kg SEL-110 + 0.2 mg/kg SEL-037), Cohort 4 (0.05 mg/kg SEL-110 + 0.4 mg/kg SEL-037), Cohort 5 (0.08 mg/kg SEL-110 + 0.2 mg/kg SEL-037), Cohort 6 (0.08 mg/kg SEL-110 + 0.4 mg/kg SEL-037), Cohort 7 (0.1 mg/kg SEL-110 + 0.2 mg/kg SEL-037), Cohort 8 (0.1 mg/kg SEL-110 + 0.4 mg/kg SEL-037), Cohort 10 (0.125 mg/kg SEL-110 + 0.4 mg/kg SEL-037), Cohort 11 (0.15 mg/kg SEL-110 + 0.2 mg/kg SEL-037), and Cohort 12 (0.15 mg/kg SEL-110 + 0.4 mg/kg SEL-037)

- Vitals at (Treatment Period 5, Day 0) predose (T-0), intradose after the start of study drug IV infusion (SEL-037) at 15, 30, 45, 60, 90, 120 and 180 minutes, then at 6 hours; and then at Day 1, 7, 14, 21 and 30 or early termination.
- ECG exam at (Treatment Period 5, Day 0) predose and End of Study Treatment Period 5, Day 30 or early termination.
- Adverse events (AE) and serious adverse events (SAE) starting at dosing. AEs will be graded according to Rheumatology Common Toxicity Criteria, version 2.0. If a severe infusion reaction occurs, a determination of anaphylaxis (Grade 4 reaction) will be based on the National Institute of Allergy and Infectious Diseases (NIAID)/ Food Allergy & Anaphylaxis Network (FAAN) Anaphylaxis Criteria.
- Concomitant medication usage will be recorded throughout the trial.
- Clinical laboratory tests (blood chemistry, hematology including clotting parameters, and urinalysis) per the Time and Events Schedule.
- Immunogenicity samples for anti-PEG antibodies at the Screening Visit and for anti-pegsiticase, anti-uricase, and anti-PEG antibodies at baseline (predose for Treatment Periods 1, 2, 3, 4 and 5), Day 7, 14, and 21 post each treatment for Treatment Periods 1, 2, 3, 4, and 5, and EOS / early termination (Treatment Period 5, Day 30).

Safety (Part C, Cohorts 13, 15, and 17):

Note: Cohorts 14 and 16 are intentionally omitted from this protocol in order to maintain the cohort numbering convention of associating odd numbered cohorts with the 0.2 mg/kg SEL-037 dose.

- Physical exam at the Screening Visit and Treatment Period 5, Day 30/early termination.

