4.4. Potential Risks and Benefits

4.4.1. SEL-037

Some subjects may have uric acid levels lowered for a brief or a longer period depending upon the subject's response to multiple doses of pegsiticase alone.

Potential risks include those that have been identified in preclinical studies and clinical studies of SEL-037 and SEL-212 as well as similar marketed products. These include 1) infusion reactions including anaphylaxis, 2) gout flares and 3) methemoglobinemia and hemolysis.

The use of biological therapeutics utilizing a protein of non-human origin is associated with the risk of immunogenicity that could result in infusion reactions including anaphylaxis. The formation of antibodies to SEL-037 was found in the animal toxicology studies. Previous human use of pegylated and unpegylated uricases have been associated with infusion reactions and anaphylaxis (Sundy, 2007; Cortes, 2010; Sundy, 2011). These adverse events would appear to be more prevalent in multiple dosing regimens but have been reported associated with the first dose presumably due to cross-reactivity or preexisting immunogenicity to the various components of the drug product or non-IgE related reactions. The current study excludes subjects with previous exposure to uricases and with preexisting immunoreactivity to PEG.

Gout flares are a potential risk in subjects with gout as therapies that reduce uric acid concentrations can produce flares. Premedication for flare will be given to subjects.

One of the byproducts of the degradation of uric acid by SEL-037 is hydrogen peroxide. Excessive oxidative stress can be detrimental to red blood cells. Serious hemolytic reactions and methemoglobinemia were reported in less than 1% of the oncology patients with tumor lysis syndrome in clinical studies with Elitek[®]. Similar events of severe hemolytic reactions have been reported with Krystexxa[®]. Subjects that are catalase or glucose-6-phosphate dehydrogenase deficient have a reduced ability to deal with oxidative stress and these subjects will be excluded.

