11.2.2.3. Adverse Event Intensity/Severity Grading

AEs will be classified according to the Rheumatology Common Toxicity Criteria, version 2.0 (Woodworth et al. 2007). The general framework for grading AEs is provided below, and the full scale is provided in Section 19.1 of the protocol.

- **Grade 1 (mild)** AE that is usually transient of short duration; or involves mild or minor symptoms which are of marginal clinical relevance; or is asymptomatic consisting of clinical or diagnostic observations alone; no intervention or only minimal treatment with non-prescription intervention was required. The event does not generally interfere with usual activities of daily living.
- **Grade 2 (moderate)** AE that is usually alleviated with additional specific therapeutic intervention. The event interferes with usual activities of daily living (e.g., shopping, laundry, transportation, or ability to conduct finances), causing discomfort but poses no significant or permanent risk or harm to the subject.
- **Grade 3 (severe)** AE that is medically significant/important but not life-threatening; may require brief hospitalization to prevent the event from worsening; interrupts usual activities of daily living, or significantly affects clinical status, or may require intensive therapeutic intervention.
- **Grade 4 (life-threatening)** An AE, and/or its immediate sequelae, which is associated with an imminent risk of death or which is associated with physical or mental disabilities that affect or limit the ability of a person to perform activities of daily living (eating, ambulation, toileting, etc.); disability may be persistent or result in significant disability, incapacity or limitation of self-care activities.

For an assessment of anaphylaxis, the clinical criteria for the diagnosis of anaphylaxis will be based on the National Institute of Allergy and Infectious Diseases (NIAID)/ Food Allergy & Anaphylaxis Network (FAAN) Symposium criteria for anaphylaxis diagnosis (Section 19.2).

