19.1.1. Clinical Signs and Symptoms

A. Allergic/Immunologic

	1 (Mild)	2 (Moderate)	3 (Severe)	4 (Life-Threatening)
A1. Allergic reaction/hypersensitivity (includes drug fever)	Transient rash; drug fever <38°C; transient, asymptomatic bronchospasm	Generalized urticaria responsive to meds; drug fever >38°C; reversible bronchospasm	Symptomatic bronchospasm requiring meds; symptomatic urticaria persisting with meds; allergy-related edema/angioedema	Anaphylaxis; laryngeal/pharyngeal edema requiring resuscitation
A2. Autoimmune reaction	Serologic or other evidence of autoimmune reaction, but patient asymptomatic, all organ function normal and no treatment is required (e.g. vitiligo)	Evidence of autoimmune reaction involving a non-essential organ or functions, requiring treatment other than immunosuppressive drugs (e.g. hypothyroidism)	Reversible autoimmune reaction involving function of a major organ or toxicity requiring short term immunosuppressive treatment (e.g. transient colitis or anemia)	Causes major organ dysfunction; or progressive, not reversible, or requires long term administration of high dose immunosuppressive therapy
A3. Rhinitis (including sneezing, nasal stuffiness, post-nasal discharge)	Transient, non-prescription meds relieve	Prescription med required, slow response to meds	Corticosteroids or other prescription med with persistent disabling symptoms such as impaired exercise tolerance	N/A
A4. Serum sickness	Transient, non-prescription meds relieve	Symptomatic, slow response to meds (e.g. oral corticosteroids)	Prolonged; symptoms only partially relieved by meds; parenteral corticosteroids required	Major organ dysfunction, requires long-term high-dose immunosuppressive therapy
A5. Vasculitis	Localized, not requiring treatment; or rapid response to meds; cutaneous	Symptomatic, slow response to meds (e.g. oral corticosteroids)	Generalized, parenteral corticosteroids required or/and short duration hospitalization	Prolonged, hospitalization, ischemic changes, amputation

B. Cardiac

	1 (Mild)	2 (Moderate)	3 (Severe)	4 (Life-Threatening)
B1. Arrhythmia	Transient, asymptomatic	Transient, but symptomatic or recurrent, responds to meds	Recurrent/persistent; maintenance prescription	Unstable, hospitalization required; parenteral meds

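### The anaphylaxis appendix steers sites towards criterion 1 at every infusion on a premise that fits only the first, and the synopsis and Section 11.2.2.3 disagree on which reactions are assessed

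*Protocol*

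**What the plan says.** Section 19.2 states that anaphylaxis is highly likely when any one "of the following 3 criteria are present", and prints all three. Item 1 needs skin or mucosal involvement plus either respiratory compromise or reduced blood pressure. Item 2 needs two or more of four features (skin-mucosal, respiratory, blood pressure, persistent gastrointestinal) after a likely allergen for that patient. Item 3 needs reduced blood pressure after a known allergen for that patient. The closing note reads "Item 1 will generally apply to subjects in this study since SEL-037 will not be a known or a likely antigen for these subjects". It names no dose or treatment period.

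On when the criteria are used, the synopsis safety list for Parts A and B says "If a severe infusion reaction occurs, a determination of anaphylaxis (Grade 4 reaction) will be based on" the NIAID/FAAN criteria; its Part C list has no matching sentence. Section 11.2.2.3 says "For an assessment of anaphylaxis, the clinical criteria for the diagnosis of anaphylaxis will be based on the National Institute" (continuing with the same NIAID/FAAN source), without reference to severity.

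SEL-037 is planned in five treatment periods; the synopsis says of premedication: "This will occur for every dose of study drug in Treatment Periods 1-5". Of infusion reactions and anaphylaxis with uricases, Section 4.4.1 says "These adverse events would appear to be more prevalent in multiple dosing regimens".

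**The concern.** The note describes a subject who has not met SEL-037. Exclusion of prior uricase exposure and of PEG immunoreactivity makes that true at entry. It stops being a safe description once the subject has been dosed, and a completer has four further infusions. A site that follows the note at those infusions will look for skin signs first and may not classify a reaction that lacks them.

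The synopsis wording adds a second filter. If only reactions already judged severe are compared with the criteria, a reaction graded moderate is not compared with them, even if it would qualify.

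Safety is the primary objective, and the SAP (Section 4.3) makes adverse event frequencies primary endpoints. The SAP has no anaphylaxis definition and no derived anaphylaxis table. Events are tabulated by preferred term, intensity and causality (SAP Section 11.3), so the site's term and grade pass straight into the results. Grade also decides whether the protocol requires a narrative (Section 12.8.2, Grade 3 or higher).

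**Working it through.** The documents give no anaphylaxis rate, so there is no figure to reproduce. The check compares passages and counts sign patterns.

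**1. Does the premise hold after the first infusion?**

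- Section 4.4.1: subjects enter without uricase exposure or PEG immunoreactivity. This supports the note at infusion 1.
- Section 4.3.2.1: after one dose in the first SEL-037 study (N=22), antibodies went with faster clearance and weaker activity at Day 14 in 3 + 2 + 3 + 2 = 10 subjects. The second dose here is due 28 days after the first.
- Sections 4.4.1 and 4.5: reactions appear more common with multiple dosing, and repeat dosing of SEL-037 is named as a risk for infusion reactions.
- Section 4.3.1.1: sensitised guinea pigs had fatal anaphylactic reactions.

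On this text, SEL-037 is fairly treated as a likely allergen (item 2) after first exposure. The text does not make it a known allergen (item 3) for every exposed subject.

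**2. What does relying on item 1 leave out?**

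Let S, R, B and G be skin, respiratory, blood pressure and gastrointestinal signs: 2^4 = 16 presence/absence patterns.

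- Item 1, S and (R or B): 3 combinations of R and B, times 2 for G = 6 patterns.
- Item 2, at least two of four: 16 − 1 − 4 = 11 patterns, which include all 6 of item 1.
- Found by item 2 but not item 1: 11 − 6 = 5, namely S+G, R+B, R+G, B+G and R+B+G.
- Item 3 adds B alone, making 12 in all, but only where SEL-037 is a known allergen for that patient and the pressure threshold is met.

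Four of the five patterns recovered by item 2 have no skin sign. The patterns are not equally likely, so these counts are not case proportions.

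**3. Can a reaction below severe meet the criteria?**

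Row A1 of Section 19.1.1 lists under Grade 2 "Generalized urticaria responsive to meds; drug fever >38°C; reversible bronchospasm". Generalized urticaria with reversible bronchospasm is skin plus respiratory, which meets item 1. Graded 2, it would not be assessed under the synopsis wording but could be under Section 11.2.2.3. Row B5 likewise puts symptomatic hypotension that responds to treatment in Grade 2. With reversible bronchospasm that is R+B, which meets item 2 without a skin sign and so could be missed on both counts.

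**4. Illustration with assumed inputs**

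Assume a per-subject anaphylaxis risk p of 1% to 5%, and a share q of 0 to 50% of cases that fail item 1 and go unclassified. The chance of counting at least one case in a 20-subject cohort is 1 − (1 − p(1 − q))^20:

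| p | q = 0 | q = 50% |
|---|---|---|
| 1% | 18.2% | 9.5% |
| 5% | 64.2% | 39.7% |

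Neither p nor q comes from the documents. The table shows only how sensitive small cohorts are to a lost classification.

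**The case against.** The strongest reply is that the formal rule is intact. The note says item 1 will generally apply, the any-one-of-three rule stands above it, and items 2 and 3 are printed in full. A reader might infer that only item 1 counts; the text does not say so. This reply stands, and the fault is discouragement, not exclusion.

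A reader might also infer that moderate reactions are never compared with the criteria. Section 11.2.2.3 has no such filter, and row A1 lists anaphylaxis as Grade 4 without one. The A1 Grade 2 cell lists urticaria and bronchospasm as separate entries, so a Grade 2 call for the pair is plausible but not fixed by the table. What remains is a conflict between two passages.

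The Day 21 uric acid rule (Section 6.3.1) limits exposure. In the SEL-212 cohorts only subjects at or below 1.0 mg/dL are redosed, and antibodies are linked to lost activity, so many subjects likely to be sensitised would not be re-exposed. This also stands. It means that treating all four later infusions of every subject as affected is not justified. The rule selects on uric acid, not antibody status, and is looser for Cohorts 1 and 2, so it reduces the problem without removing it.

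Finally, the decision rules do not turn on the label. Cohort continuation refers to the rate of infusion reactions (Section 6.3), committee review to related SAEs (Section 6.3.2), and the more serious forms of bronchospasm and hypotension are already Grade 3 or 4. Signs, vital signs and the suspected-reaction samples in Table 12 are collected whatever the grade. That is right: the risk is of misclassification, not of lost data.

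**Conclusion.** The note is wrong as written for re-exposures, and the synopsis and Section 11.2.2.3 need reconciling. Both faults act in one direction, towards fewer reactions classed as anaphylaxis. The size cannot be stated: no document gives an anaphylaxis rate, the share of cases without skin signs, or how sites read the note. It is therefore not shown that anaphylaxis is under-counted, only that the wording makes this possible in a trial whose primary objective is safety.

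The conclusion rests on reading a previously exposed subject as having a likely allergen, which the protocol's antibody and repeat-dose text supports. It does not extend to item 3 from the second infusion onwards: one exposure does not make SEL-037 a known allergen for that patient, so isolated hypotension cannot be counted as missed on exposure alone.

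**What to change.** - Section 19.2: delete the note or limit it to the first SEL-037 infusion. State that all three items are assessed at every infusion, that SEL-037 is treated as a likely allergen (item 2) after first exposure, and that item 3 is used only where it is a known allergen for that patient.
- Synopsis and Section 11.2.2.3: reconcile them so that the criteria are applied to every suspected infusion reaction in all parts, whatever its initial grade. The severity condition to remove is in the synopsis; Section 11.2.2.3 needs only the scope stated.
- CRF: record which item was met.

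This concerns classification only and changes no dosing or treatment instruction. The cost is a few sentences and one CRF field, using signs already collected. The reported anaphylaxis count may be higher as a result.

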19.3. Reconstitution and Dilution for Infusion Instructions

19.3.1. SEL-037 Instructions

Follow instructions below:

1. Convert weight of subject to kg, as needed (weight in pounds divided by 2.2046).
2. Calculate the mL of reconstituted SEL-037 required for a subject

Volume (ml) reconstituted SEL-037 required for each infusion =

(dose in mg/kg) x (subject weight in kg) / (concentration of SEL-037 per ml in vial i.e., 6 mg/mL)

3. Since each vial, once reconstituted, will yield about 1 mL of product that can be withdrawn from the vial, the number of vials required for a subject equals the number of ml of reconstituted SEL-037 needed for the infusion rounded up to the next whole number.
4. Reconstitute the required number of vials each with 1.1 mL of room temperature sterile water for injection, USP. Invert (don't shake) each vial several times to ensure product is reconstituted. Do not use any vials with visible clumping. Reconstituted SEL-037 should be diluted as in Step 5 as soon as possible but reconstituted SEL-037 is stable at room temperature and normal light conditions for 8 hours.
5. Dilute required volume of reconstituted SEL-037 by adding it to 100 mL of 0.9% saline for injection, USP.
6. Infuse total volume of the SEL-037-normal saline solution over 60 minutes (+/- 2 minutes). If necessary the infusion time may be extended in order to ensure the infusion of the study medication in entirety. The SEL-037-normal saline solution is stable for up to 6 hours at room temperature (i.e., the infusion should be completed within 6 hours of dilution) but it is recommended that the infusion of SEL-037 be started as soon as possible to account for any potential interruptions in dosing. No infusion of the SEL-037-normal saline solution should start if 5 hours have lapsed between diluting SEL-037 and the start of infusion.
7. At the conclusion of the infusion, using the port closest to the IV pump, flush the IV drip set using a volume of 0.9% normal saline equal to the prime volume of the tubing.

Example for subject weighing 200 pounds in Cohort 2 (0.4 mg/kg group)

Step 1: If not already done convert weight to kg:	$= 200 \text{ pounds} / 2.2046 = 90.7 \text{ kg}$
---	---

Step 2: Calculate volume of reconstituted SEL-037 needed:	$= (0.4 \text{ mg/kg}) \times (90.7 \text{ kg}) / (6 \text{ mg/mL})$
---	--

Study: SEL-212/201 Version: 7.1	Effective Date March 19, 2018
------------------------------------	----------------------------------

$= 36.29/6 = 6.0 \text{ mL}$	
Step 3: number of vials needed:	$= \text{Round up } 6.048 \text{ mL} = 7 \text{ vials}$
Step 4 and 5: Reconstitute 7 vials and add 6.0 mL to 100 mL of 0.9% normal saline for injection, USP.	
Step 6: Infuse 106.0 mL over 60 minutes (+/- 2 minutes). If necessary the infusion time may be extended in order to ensure the infusion of the study medication in entirety	
Step 7: At the conclusion of the infusion, using the port closest to the IV pump, flush the IV drip set using a volume of 0.9% normal saline equal to the prime volume of the tubing	

